6.1.4. Methods and Equipments for Endpoints Recordings

6.1.4.1. Ocular evaluations

Ocular evaluations will be performed on both eyes. The assessments must always be performed according the sequence (1 – 10) detailed in § 6.1.3. The assessment will be performed at visit 1 (day 1), 2 (day 15±2), 3 (day 22±2))/early termination visit.

The ophthalmological assessment will include:

1. **Visual analogue scale (VAS):** Local ocular tolerability score: A global ocular discomfort score will be determined using a 100 mm VAS
2. **Symptom Assessment in Dry Eye (SANDE):** Subjects with SANDE overall score ≥ 30 mm are eligible for enrolment\randomization. The SANDE questionnaire is a short questionnaire to evaluate both dry eye intensity and frequency by using a 100 mm VAS.
3. **Best corrected distance visual acuity (BCDVA):** Subjects with best corrected distance visual acuity (BCDVA) score of ≥ 0.1 decimal units in both eyes are eligible for enrolment\randomization. Refraction and visual acuity measurements will be performed for all subjects by trained vision examiners only.

Equipment: Refraction equipment required includes:

- Retroilluminated Light box and ETDRS 4 meter distance acuity chart set
- Trial lens frames
- Trial lens set with plus or minus cylinder lenses
- Jackson cross-cylinders of 0.25, 0.50, and 1.00 diopters
- Pinhole occluder
- Tissues or eye pads and tape
- A 1 meter rigid measuring stick

4. **Slit lamp examination (SLE):** The slit lamp examination must be performed before the instillation of any dilating or anesthetic eye drops or the fluorescein agent.

The subject will be seated at the slit lamp while being examined. Grading of the eyelids, 1 lashes, conjunctiva, cornea, lens, iris and anterior chamber will be done.

5. **Central corneal sensitivity by Cochet-Bonnet aesthesiometry:** The Cochet-Bonnet aesthesiometer contains a thin, retractable, nylon monofilament that extends up to 6 cm in length. Variable pressure can be applied to the cornea by adjusting the monofilament length. The monofilament length ranges from 6 to 0.5 cm. As the monofilament length is decreased the pressure increases from 11 mm/gm to 200 mm/gm.

Corneal sensation will be measured in the affected eye(s) in the central area of the cornea using a Cochet Bonnet aesthesiometer before the instillation of any dilating or anesthetic eye drops.

Start the procedure by testing the corneal sensitivity within the area (center) of the PED or corneal ulcer of the affected eye.

Steps for using the Cochet Bonnet aesthesiometer:

1. Extend the filament of the aesthesiometer to full length of 6 cm. Slowly advance the monofilament towards the eye until the tip perpendicularly touches the corneal surface. Continue to exert a slight pressure until obtaining an inflection deviation of the filament of about 4% (i.e. the first visible inflection). If a positive reaction to the touch of cornea is elicited proceed to step 3. If a positive reaction is not achieved proceed to step 2. (NOTE:

A positive response is any action indicating corneal sensation whether communicated verbally or physically).

2. Retract the filament incrementally in 0.5 cm and repeat this step until the patient gives a positive reaction indicating that the contact of the monofilament on the cornea has been sensed. (NOTE: The shorter filament lengths indicate decreased corneal sensation).
3. Record the length of the filament in cm at which the patient sensed the contact with the cornea.
4. Repeat steps 1-3 in each of the 4 corneal quadrants (superior nasal, inferior nasal, superior temporal and inferior temporal) outside the area of the PED or corneal ulcer in the affected eye and in each of the 4 corneal quadrants of the non-affected eye.
5. To clean the instrument refer to your national standards for devices that contact the eye and tears or follow the suggested manufacturer's recommendations.

The length of the filament in cm at which the patient corneal sensation was observed for the tested area of the cornea will be entered into the eCRF.

6. **Tear collection for Lubricin dosing:** tear collection will be performed using tear wash technique with 40 µL of sterile saline solution. Dompé farmaceutici s.p.a. will be responsible for samples collection and dosing procedure.
7. **Tear Film Break Up Time (TFBUT):** TFBUT will be measured by determining the time to tear break-up. The TFBUT will be performed after instillation of sodium fluorescein solution into the inferior conjunctival cul-de-sac of each eye.
8. **Corneal fluorescein surface staining (Oxford score):** The corneal fluorescein staining will be graded by using the Oxford scheme to assess cornea and conjunctiva epithelium damage. It will be performed after instillation of sodium fluorescein into the inferior conjunctival cul-de-sac of each eye with the aid of a slit lamp at 10X magnification using cobalt blue illumination.
9. **Schirmer's test (ST) I (without anaesthesia):** Schirmer strips (Manufacturer: Contactcare Ophthalmics & Diagnostics; distributor: Alfa Intes S.r.l., [name]) will be used.

This test will be performed to measure aqueous tear secretion prior to the instillation of any dilating or anesthetic eye drops. Both eyes may be tested at the same time.

This test will be conducted in a dimly lit room.

10. **Intraocular pressure (IOP):** IOP may be performed using either Goldmann applanation tonometry after the instillation of a topical anesthetic.

IOP should be measured in both eyes after completion of all other slit lamp examinations to avoid potential interference with the other evaluations.

All examinations and assessments that will be carried out during this study are non-invasive, are commonly used in the management of subjects with dry eye and pose no risk to the subjects. Subjects might feel a slight discomfort during the execution of the Schirmer test and a local allergic reaction or irritation from the use of fluorescein may be observed.

6.1.5. Subjects Replacement

Discontinued subjects will not be replaced. Any patient who exits early from the study must undergo all procedures outlined in Visit 3.

6.2. ID AND COMPARATORS

6.2.1. Description and Justification of ID/Comparator Exposure

During the 2 week (15±2 days) double-masked, randomized, controlled treatment period, (hereafter, also referred to as the controlled treatment period) enrolled subjects will be randomized at baseline in a 1:1:1 ratio to the experimental treatment arm (Lubricin 20 µg/ml or Lubricin 50µg/ml, one drop TID for two weeks) or the control arm Vismed® 0.18% (sodium hyaluronate eye drop solution, one drop TID for two weeks).

During the follow-up period at the discretion of the treating physician any ocular topical treatment is allowed, including other artificial tears/lubricants.

Investigational Medical Devices will be administered by ocular route according to 1:1:1 randomization. If the subject forgets to take the study drug, it should be taken as soon as the subject remembers.

The proposed duration of the treatment has been considered as adequate to support local tolerability, safety and efficacy of the product in comparison with the selected control.

6.2.2. Justification of the Choice of Comparator

HA 0.18% eye drops are one of the most used ocular lubricant for moderate dry eye patients.

The presentation of the control has been selected to ensure complete masking of the CI.

6.2.3. Number and Justification of the IDs Used

The tolerability, safety and efficacy profile of LUBRICIN EYE DROPS will be compared with HA 0.18% (Vismed® multidose) one of the most used eye drops in relieving eye dry symptoms.

During the follow-up period at the discretion of the treating physician any ocular topical treatment is allowed, including other artificial tears/lubricants.

Each subjects will receive enough quantity of IDs to complete the study, in case of loss of samples by the subject/s, and after an enquiry, Dompé will provide sufficient amount of samples in surplus over the minimum required for full treatment.

6.3. SUBJECTS

The subject selection criteria will be checked at the Day 1 baseline Visit (Visit 1).

6.3.1. Inclusion criteria for Subject Selection

1. Patients 18 years of age or older.
2. Patients undergone ocular refractive surgery within 6 months from Day 1 Visit.
3. Patients with ocular discomfort defined as SANDE score ≥ 30 at baseline.
4. Average VAS score (dryness, foreign body sensation, burning/stinging, itching, pain, stick feeling, blurred vision and photophobia) ≥ 25 mm;
5. Best corrected distance visual acuity (BCDVA) score ≥ 0.1 decimal units in both eyes at the time of study enrolment.
6. Only patients who satisfy all Informed Consent requirements may be included in the study. The patient and/or his/her legal representative must read, sign and date the Informed Consent document before any study-related procedures are performed. The Informed Consent form signed by patients and/or legal representative must have been approved by the IEC for the current study.

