3. STUDY DESIGN JUSTIFICATION

Laser refractive surgery for the correction of refractive errors has become an affordable and safe procedure. However, a large number of patients complain of ocular surface symptoms after refractive surgery. In fact, both photorefractive keratectomy (PRK) and laser in situ keratomileusis (LASIK) can induce or exacerbate dry eye, that manifests as an increase in degree and frequency of symptoms, corneal findings, such as superficial punctate keratopathy, and abnormal results of dry eye tests, such as the Schirmer test and tear break-up time. The cause mainly involves decreased corneal sensation, resulting in decreased feedback to the lacrimal gland and reduced tear production. Other causes may include increased evaporation, inflammation, or toxicity of medications. Dry eye symptoms are usually transient, lasting only a few weeks, but in a significant percentage of patients these symptoms can last up to 1 year. ([17](#)).

In addition, refractive surgery procedures have been described to exert a neurotrophic damage to the cornea, along with other changes in corneal shape, that affect tear dynamics causing ocular surface alterations. As a consequence, symptoms of dryness may occur in more than 50% of patients after LASIK, with other complications such as fluctuating vision, decreased best corrected visual acuity, and severe discomfort occurring in approximately 10% of patients ([18](#)).

As a consequence of the widespread use of refractive surgery, a safe and non-toxic treatment that can improve ocular surface symptoms after the procedures is highly sought after by patients and clinicians.

Lubricin, also called Proteoglycan 4 (PRG4), is a mucin-like glycoprotein originally discovered in synovial fluid, as a secreted product of cells that line the joint tissues, which is present at the surface of articular cartilage.

In vitro studies have shown that lubricin in saline buffer acts as a lubricant between various surfaces, as well as in synovial fluid, providing evidence that lubricin is a principal lubricating protein in joints. Besides the lubricating property, lubricin has been shown to exert anti-adhesive action, strain energy dissipation, and a protective effect on underlying cells.

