6.3.2. Exclusion criteria for Subject Selection

1. Patients with a severe Dry Eye condition (severity level 4 according to the Report of the International Dry Eye Workshop -DEWS, 2007)
2. Best corrected distance visual acuity (BCDVA) score of < 0.1 decimal units in either eye at the time of study enrolment
3. Evidence of an active ocular infection in either eye
4. History or presence of ocular surface disorders other than ocular discomfort in either eye
5. Use of any ocular topical medication other than the study medications for the treatment of ocular diseases including artificial tears during the study period
6. Use of topical cyclosporine, topical corticosteroids or any other topical medication for the treatment of dry eye in either eye within 30 days of study enrolment
7. History of any ocular surgery (excluding laser or refractive surgical procedures) in either eye within 30 days before study enrolment. Ocular surgery will not be allowed during the study treatment period and elective ocular surgery procedures should not be planned during the duration of the follow-up period
8. Known hypersensitivity to one of the components of the study or procedural medications
9. Participation in another clinical study at the same time as the present study or within 90 days of screening/baseline visit
10. History of drug, medication or alcohol abuse or addiction.
11. Females of childbearing potential (those who are not surgically sterilized or post-menopausal for at least 1 year) are excluded from participation in the study if they meet any one of the following conditions:
 - a. are currently pregnant or,
 - b. have a positive result on the urine pregnancy test at the Screening/Baseline Visit or,
 - c. intend to become pregnant during the study treatment period or,
 - d. are breast-feeding or, not willing to use highly effective birth control measures, such as: Hormonal contraceptives – oral, implanted, transdermal, or injected and/or mechanical barrier methods – spermicide in conjunction with a barrier such as a condom or diaphragm or IUD during the entire course of and 30 days after the study treatment periods.

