6.3 Randomization

The randomization list was computer-generated by the CRO Biometry Unit, using the PLAN procedure of the SAS® version 9.3 (TS1M1) (6) according to the following specification:

- Randomization scheme: 1:1:1
- Block size: 6
- Stratification factors: None

The randomization list will be attached to the final clinical study report.

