8.11 Efficacy analysis

8.11.1 Primary efficacy analysis

The primary efficacy analysis will be performed on the subjects included into the Full Analysis Set.

Subjects will be analysed according to the treatment they actually received.

8.11.1.1 Tolerability using a Visual Analogue Scale (VAS) for dryness, foreign body sensation, burning/stinging, itching, pain, stick feeling, blurred vision and photophobia

The VAS values of each ocular symptom (i.e. dryness, foreign body sensation, burning/stinging, itching, pain, sticky feeling, blurred vision and photophobia) and their changes from day 1 - pre-dose values and day 15±2 - pre-dose values for the study/primary eye and for the non-study/secondary eye will be listed ([Listing 16.2.6.1](#)) and summarised by treatment and time point using descriptive statistics (mean, SD, CV%, minimum, median and maximum) ([Table 14.2.1.1](#)).

The VAS values of each ocular symptom for the study/primary eye and for the non-study/secondary eye will be analysed using an analysis of variance for repeated measures model. The model will include fixed effect terms for time point, baseline covariate (i.e. the day 1 - pre-dose value) and treatment. Time point will be specified as a repeated measurement. An unstructured covariance structure of the R matrix will be used and covariance parameters will be estimated using the restricted maximum likelihood method ([Table 14.2.2.1](#)).

Only the VAS values collected at Visit 1, Visit 2 and Visit 3 will be included into the analysis of variance for repeated measure model.

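### Time since refractive surgery, a plausible prognostic factor on the protocol's own account, enters neither the randomisation nor any planned between-arm analysis

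*Protocol*

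**What the plan says.** - **Entry window.** Inclusion criterion 2 (Protocol 6.3.1, repeated in SAP 4.4) requires "Patients undergone ocular refractive surgery within 6 months from Day 1 Visit". This is an upper limit only.
- **No minimum interval.** Exclusion criterion 7 (Protocol 6.3.2) covers "History of any ocular surgery (excluding laser or refractive surgical procedures) in either eye within 30 days before study enrolment", so refractive surgery is exempt from the 30-day rule. Exclusion criterion 6 bars "Use of topical cyclosporine, topical corticosteroids or any other topical medication for the treatment of dry eye in either eye within 30 days of study" entry. That rule concerns medication, although it may keep out some recently operated patients.
- **Natural history.** Protocol section 3 describes the symptoms as "usually transient, lasting only a few weeks, but in a significant percentage of patients these symptoms can last up to 1 year".
- **Symptom threshold.** Entry also needs "Patients with ocular discomfort defined as SANDE score ≥ 30 at baseline" and an average VAS of at least 25 mm. Both measure severity on the day and say nothing about its course.
- **Randomisation.** SAP 6.3 gives 1:1:1 allocation in blocks of 6 with "Stratification factors: None".
- **VAS analysis.** SAP 8.11.1.1: "The model will include fixed effect terms for time point, baseline covariate (i.e. the day 1 - pre-dose value) and treatment".
- **Secondary endpoints.** SAP 8.11.4.1–8.11.4.5, 8.11.4.7 and 8.11.4.8 compare Day 15 changes by unadjusted Student's t tests. Slit lamp scores (8.11.4.6) use the Wilcoxon rank sum test. SAP 8.11.2 and 8.11.3 plan no sensitivity or subgroup analysis.
- **Background tables.** SAP 8.7.9 codes surgeries in MedDRA and tabulates them by arm at preferred-term level. The visible text plans no summary of the interval since surgery.
- **Control.** The only comparator is active (hyaluronate 0.18%). There is no untreated or vehicle arm.

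**The concern.** The protocol's rationale describes two kinds of patient: the majority, whose symptoms settle in weeks, and a substantial minority, whose symptoms persist for months. Both can enter. Someone a few weeks from surgery is more likely than someone at month 6 to improve over 15 days whatever is instilled. That makes time since surgery a plausible predictor of the quantity being compared. Day 1 VAS does not replace it, because two subjects with the same score can be on different courses.

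Two things are at stake:
- With 10 per arm, a chance excess of recently operated subjects in one arm would look like a product difference in VAS, SANDE, staining, TFBUT or corneal sensitivity.
- The tabulated within-arm changes from baseline will include spontaneous recovery, and nothing in the design separates it out. Protocol 5.2 expects both products to reduce symptoms, so a reader could take those tables as support for that expectation.

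**Working it through.** **Inputs from the documents.** SAP 8.4.1: SD of VAS change 10 mm, expected change −20 mm in every arm, target half-width 9 mm, two-sided 95% interval. Protocol 6.3.7: 10 per arm.

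**Assumptions, not in the documents.** Entry times uniform over 0–26 weeks; a fraction q = 0.25 to 0.50 of subjects still recovering; extra natural improvement R = 10 to 20 mm over two weeks in those subjects and none in the others.

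**1. The plan's own figure.** N = ceiling(2 × 10² × 1.96² / 9²) = ceiling(9.49) = 10 per arm, as stated. At N = 10 the half-width is 1.96 × 10 × √(2/10) = 8.8 mm.

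**2. Imbalance in time since surgery.** SD of a uniform 0–26 week variable = 26/√12 = 7.5 weeks. SD of the difference between two arm means = 7.5 × √(2/10) = 3.4 weeks. The chance that two given arms differ by more than 4 weeks is 23% by normal approximation and 24% by simulation. For at least one of the two Lubricin–hyaluronate pairs it is 39%.

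**3. Imbalance in recovering subjects.** With binomial(10, q) counts in each arm, a difference of three or more between two given arms has probability 0.19 at q = 0.25 and 0.26 at q = 0.50. Three subjects in ten shift the difference in means by 0.3 × R, which is 3 mm at R = 10 and 6 mm at R = 20.

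**4. Precision.** The recovery variance is R² × q(1 − q), from 18.75 mm² (R = 10, q = 0.25) to 100 mm² (R = 20, q = 0.50).
- If the SAP's 10 mm SD already contains this spread, the half-width stays 8.8 mm.
- If it comes on top, the total SD is √118.75 = 10.9 mm to √200 = 14.1 mm, and the half-width is 9.6 to 12.4 mm.

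**5. Natural recovery within an arm.** The mean contribution is q × R, from 0.25 × 10 = 2.5 mm to 0.50 × 20 = 10 mm, against the −20 mm the SAP expects.

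**6. What adjustment could recover.** This depends on how tightly recovery follows time.
- *Sharp cut-off: everyone within the first q of the window recovers and nobody later does.* A linear covariate explains 3q(1 − q) of the recovery variance, 56% at q = 0.25 and 75% at q = 0.50. A log covariate explains q(ln q)²/(1 − q), 64% and 48%.
- *Loose dependence: the probability of recovery falls linearly from a to b over the window.* A linear covariate explains [(a − b)²/12] / [m(1 − m)], with m the mean of a and b. From 0.8 to 0.2 this is 12%, from 0.5 to 0 it is 11%, and from 0.6 to 0.2 it is 6%.

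As an example, take R = 10 and q = 0.50, a recovery variance of 25 mm². If it is added to the 10 mm SD, removing 12% or 75% of it takes the half-width from 9.8 mm to 9.7 or 9.0 mm. If it lies within the 10 mm SD, the half-width goes from 8.8 mm to 8.6 or 7.9 mm.

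**The case against.** The strongest reply is that the trial is randomised against a concurrent control. Recovery is balanced in expectation, and the chance imbalance in steps 2 and 3 is what the confidence interval already allows for. That stands. A reader might infer that the Lubricin–hyaluronate comparison is biased; the design does not support that. The loss is in precision and in how one realised allocation is read.

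Other points on that side also stand, in whole or in part:
- SAP 8.3 calls the trial exploratory, with no regulatory claim resting on it, and no within-arm test is planned. The caution about within-arm change is therefore about interpretation and does not correct a stated analysis.
- SAP 8.4 says its planning values rest on no clinical or literature data, so the 10 mm may or may not include recovery spread. Quoting only the 9.6–12.4 mm half-width would be one-sided.
- The 25–50% and 10–20 mm inputs are assumptions. At the top end, natural recovery alone equals the whole change the SAP expects on treatment.
- The medication exclusion may remove some very early cases. Entry within days of surgery is permitted, but the documents do not show how common it would be.
- Adverse events, and VAS changes at 15 and 30 minutes from the same day's pre-dose value, should be largely unaffected by recovery over weeks.

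A reader might also infer that adjustment would recover most of the lost precision. Step 6 shows that this needs a sharp time cut-off. The protocol's statement that symptoms can persist for up to a year in many patients points to a looser link, where the gain is small. Nor is surgical procedure ignored: SAP 8.7.9 already tabulates surgeries by arm. Only the interval is missing.

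**Conclusion.** The point holds as a matter of efficiency and interpretation. The protocol itself identifies a plausible prognostic factor for two-week change, the timing is needed anyway to verify inclusion criterion 2, and no planned comparison uses it.

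On the stated assumptions, two given arms differ by more than 4 weeks in mean time since surgery in about 23–24% of trials. An imbalance of three or more recovering subjects occurs in 19–26% and moves the VAS difference by at least 3–6 mm. The half-width is 8.8 mm or 9.6–12.4 mm, according to whether the planned SD already includes recovery. Adjustment would remove between about 6–12% and about 50–75% of the recovery variance.

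The absence of any use of time since surgery, and the inability to separate natural recovery from within-arm change, do not depend on those assumptions. The sizes do. Neither the sample size nor the validity of the randomised comparison is called into question.

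**What to change.** Amend the SAP before unblinding:

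1. **8.11.1.1.** Add time from refractive surgery to Day 1 as a covariate in the VAS model, in one functional form fixed now (for example log weeks). Choosing the scale after seeing the data would not be pre-specification. Use the surgery date of the eye being analysed, and say how a fellow eye without refractive surgery is handled.
2. **8.11.4.** For the endpoints now compared by t test, give an ANCOVA of the Day 15 change with treatment, baseline value and time since surgery. SANDE is not analysed by eye, so use the study/primary eye's date. Leave the slit lamp Wilcoxon tests as they are.
3. **8.7.** Summarise time since surgery by arm, beside the existing surgery table in 8.7.9.
4. **Reporting.** State that within-arm change from baseline is descriptive and is not evidence of product effect. Rest efficacy statements on the adjusted between-arm difference.

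Eligibility, treatment and visits do not change. Surgical history is already taken at Visit 1, so the work is SAP text plus the programming to replace seven t-test analyses with ANCOVA. The statistical cost is about one degree of freedom among 30 subjects for the added covariate. If time since surgery predicts change only weakly, the gain in precision will be small; the by-arm summary is useful either way.
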